Mitochondrial isolation, content, function, and oxidative stress: Respirometry of muscle tissue will be performed in isolated mitochondria by the method of Anderson et al⁷⁰ using the Oxygraph O2K respirometer. Portions of muscle tissue will be immediately homogenized and fresh mitochondrial preparations will be used to determine carbohydrate and lipid oxidation rates. Remaining tissue will be flash frozen in liquid nitrogen for appropriate analyses. Viable mitochondria will be isolated from fresh skeletal muscle tissue by trypsin collagenase digestion, homogenization and differential centrifugation by the methods developed by [name], consulting mentor. Mitochondrial protein concentrations will be determined using a bicinchoninic acid (BCA) assay. For mitochondrial assays, viable mitochondria will be introduced into the Oxygraph O2K chambers in duplicate with sequential addition of a combination of lipid and carbohydrate

substrates as well as physiological and chemical uncouplers, activators and inhibitors to gain a comprehensive view of metabolic and mitochondrial function in the physiological and supraphysiological energy states. A portion of the viable mitochondria isolated from the fresh tissue samples will also be used to assess hydrogen peroxide (H_2O_2) emission in the presence of the same substrates that were used in the mitochondrial respiration experiments. H_2O_2 is a common product of superoxide degradation and will be measured using a standard kit assay (Amplex Red®, Invitrogen), modified for mitochondria. A portion of the frozen tissue sample will be used to measure glutathione levels using a standard kit (Bioxytech® GSH/GSSG- 412TM, OxisResearch). The ratio of reduced to oxidized glutathione is a standard indicator of oxidative stress. Mitochondrial content is measured by QRT-PCR and blue native gel electrophoresis of isolated mitochondria.

Study drug: Metformin and placebo will be provided by Caraco Pharmaceutical Labs as indicated above. They will be given in fixed order single-blinded fashion. To minimize GI side effects, study drug will be given in a forced uptitration with 500 mg once daily for one week, twice daily for one week, and then the higher dose (1000 mg) for the remainder of the 6 week intervention. Subjects who fail to tolerate an uptitration will be held at the prior dose for an additional 3 days and then retried. Subjects who have not reached at least 500 mg BID dosing by the end of week 3 will be withdrawn from the study. Thus, final metformin dosing will be 500 BID or 1000 BID.

DEXA (Dual-energy X-Ray Absorptiometry): Body composition and bone mineral density will be measured using the DEXA technique⁷¹. This technique relies on the absorption of dual electron wavelengths for the assessment of body fat, lean tissue, and bone mineral density. During the procedure, the subject will be supine on the measurement table, and the arm of the machine will slowly pass over their body. Body fat distribution will be determined using the waist-to-hip ratio where the waist circumference is measured 1/2 the distance from the lowest point of the ribs to the iliac crest and the hip circumference is measured at the level of the greater trochanter.

Diet Instruction and diet lead-in: Customary macronutrient pattern and diet preferences will be ascertained by an online diet questionnaire provided by the CCTSI Nutrition Core team. A three day diet will be provided by the CTRC prior to both study visits. A CTRC dietician will prescribe a standardized nutrient breakdown including 25% protein, 35% fat and 40% carbohydrate for the three days prior to visits 5 and 8. The sodium in the diet will be limited to ≤ 2300 mg/day.

Immunoblot analysis: Frozen muscle biopsies are weighed, cut into 30mg sections, homogenized, solubilized, centrifuged, assayed for protein concentration, subjected to electrophoresis (50 μ g), and transferred to membranes (Bio-Rad). Blots are exposed to appropriate antibodies. Immunoreactive products are detected using enhanced chemiluminescence and exposure to film, quantified, and normalized to an internal standard.

Quantitative Real Time PCR: Quantitative real-time PCR is performed with the Roche LightCycler 480 instrument and 480 SYBR Master mix for total mitochondrial DNA. Primer specificity is confirmed by melt curves. Relative abundance of mitochondrial DNA is quantified by standard curve method and normalized to the 18S rRNA gene as a chromosomal DNA marker.

³¹P-MRS: Methods: Calf MRS123-126: a 3.0 T whole-body MRI scanner (GE Medical Systems, Waukesha, WI), with a dual frequency ³¹P/¹H Flex Coil (Clinical MR Solutions) creates scout images of the dominant leg gastrocnemius and soleus muscles. The widest cross sectional area is fitted in the equation described in our preliminary results to determine expected force. A resistance strap is affixed to the hips, dominant leg, ankle and foot, on a specialized portable, in-MRI exercise bench to allow isolated static plantar flexion against force. Flexion is done at 70% of the subject's predicted maximal force for 90 seconds, monitored by a Single Point Load Cell (Teda Model 1250), connected via an A/D board to a laptop for analysis on LabView software. After scout images and shimming using the ¹H portion of the flex coil, ³¹P measurements are made at rest, during calf exercise, and for at least 15 min immediately following the exercise bout (figure 5). Total study time is < 1 hour. Output is analyzed using JmRUI and Sigma Stat to calculate PCr, phosphate (Pi), ADP, and ATP, which are used to calculate pH, ADP t_{1/2}, PCr t_{1/2}, Pi t_{1/2}, and substrate dependent (VPCr, Qmax, the apparent mitochondrial capacity i.e. maximal oxidative ATP production rate; anaerobic glycolysis; oxidative phosphorylation; CK, the non-mitochondrial dependent ATP production from creatinine kinase; muscle efficiency) and oxygen-dependent components (time constant for PCr, Pi & ADP recovery), allowing differentiation of substrate vs. oxygen-dependent causes of mitochondrial dysfunction. Primary outcomes for this portion of this sub-study will be QMax (max oxidative ATP production rate) and ADP depletion half-time.

Risks:

Continuous glucose monitoring: The continuous glucose monitor involves a small catheter placed under the skin in the area to the side of your belly. Potential risks of this procedure include bleeding, infection, pain, and catheter placement into a muscle causing pain and bruising.

Blood Draws: Pain may be felt when the needle goes into the vein. A bruise may form at the site. There is a risk of infection. Standard precautions will be used to minimize these risks and only CTRC nurses will perform blood draws.

Fasting: Subjects who are taking insulin run a risk of hypoglycemia during fasting. Fasting will only be required during the inpatient stays. Symptoms listed above will be described in advance and subjects will be monitored closely.

DEXA: During DEXA testing the amount of radiation received is less than 25mRem total body equivalent dose per measurement. This is estimated to be less than one-half the amount received from a chest x-ray. The radiation in this study is not expected to greatly increase these risks, but the exact increase in such risk is not known. Women who are or could be pregnant should receive no unnecessary radiation, and should not participate in this study.

IV Risks: When the needle carrying the plastic tube goes into a vein, it hurts for a short time. The needle is then removed and only the plastic tube remains in the vein. There will also be the minor discomfort of having the plastic tube taped to the arm. In about one in 10 cases a small amount of bleeding under the skin will produce a bruise. The risk of a blood clot forming in the vein is about one in 100, while the risk of infection or significant blood loss is one in 1000. Standard precautions will be used to minimize risk and only trained CTRC personnel will place IVs.

Arterial stiffness measurement and HRV measurements: There is a very slight chance that fainting or stroke may occur. No actual fainting or stroke have ever been reported. The risk of these happening has been estimated to be less than 1/1,000,000.

Brachial Artery FMD: There may be a slight discomfort while the arm cuff is inflated.

Muscle Biopsies: May be uncomfortable or cause pain. Infection, bleeding, or damage to nerves is reported to be 1/1000. The incision will be closed with a steri-strip or, if necessary, a single suture. A bruise may result temporarily, but a scar may be permanent. Numbing medicine will be used to reduce the pain. Rarely this causes an allergic reaction. A total of 2 muscle biopsies is required. Soreness or cramping in the muscle can occur during or after the procedure. Sometimes people faint.

Indirect calorimetry: Some people experience feelings of claustrophobia under the plexiglass hood used for these measurements.

Insulin Clamp: With the insulin clamp there is the risk of hypoglycemia. The symptoms of hypoglycemia are excessive sweating, faintness, headache, pounding heart, trembling, and impaired vision. Under very extreme degrees of hypoglycemia, a person may lose consciousness. Blood glucose levels will be monitored throughout this test to prevent hypoglycemia from occurring. I have performed >50 clamps and have caused no episodes of symptomatic hypoglycemia.

Echocardiography: This is a noninvasive ultrasound tests with no significant risk or discomfort. There may be slight pressure from the wand over the chest area and women may feel uncomfortable about the having the wand placed and held near the breasts.

Metformin: Though metformin is generally well tolerated, there is the potential for side effects/adverse reactions. With metformin there is a small risk of a serious allergic reaction with anaphylaxis (difficulty breathing, swelling of lips, face or tongue). Milder allergic reactions with rash also occur. Metformin is contraindicated in anyone with a history of lactic acidosis or renal insufficiency (Cr >1.5(males) or 1.4 mg/dL (females)) because of the risk of acidosis. This would present as shortness of breath, muscle or bone pain, dark urine, and/or fever. The most common side effects with metformin are headache and GI side effects including abdominal pain, nausea, vomiting, diarrhea, loss of appetite, abdominal bloating/discomfort, and flatulence. These are reported in some literature in up to 50% of patients. However, with a low mealtime starting dose and slow uptitration, this risk is much lower and can be largely avoided. The PI has considerable experience with metformin and has found that with the planned up titration <10% of patients do not tolerate metformin. Some attrition due to GI side effects is expected in this study.

For these subjects with diabetes and on insulin there is also a risk of hypoglycemia, especially through the start and uptitration of metformin. Subjects will continue to do their normal blood sugar checks. In

addition, their CGM monitors will be downloaded weekly for review of blood sugars and insulin dose adjustment if needed by the PI. Subjects are well aware of the symptoms of hypoglycemia and will be advised to check their blood sugar for any symptoms.

Though metformin is frequently taken during pregnancy, it is not fully proven safe in pregnancy and we will be excluding subjects who are pregnant or planning to get pregnant. Therefore, a pregnancy test will be done with the initial screening labs, and if a subject is pregnant or breastfeeding, she will be excluded from this study. If a subject becomes pregnant during the study she will be instructed to notify the study coordinator and withdraw from the study.

³¹P-MRS: Subjects may develop claustrophobia in the magnet or mild muscle cramping during the exercise portion

Unforeseen Risks: This study may include risks that are unknown at this time.

E. Potential Scientific Problems:

Interpretation of results/pitfalls and limitations: This study addresses the question of whether metformin affects insulin action and vascular and mitochondrial sequelae of IR in T1D. Based on the literature, I expect that GIR will be increased by this intervention, though it is unclear whether this will be mediated through changes in classical insulin signaling. An improvement in GIR would support the hypothesis that metformin is a viable approach to the treatment of IR in T1D that may have CVD benefits similar to those seen in T2D. If cardiovascular and/or mitochondrial measures improve (with or without changes in IR), this also lends support to metformin as a potentially CVD protective intervention and provides data to support a longer study looking at clinical outcomes. If no change in GIR or vascular measures occurs, this would suggest that IR and CVD risk in T1D are mechanistically different from other populations, an exciting result in itself, and future efforts would explore other mechanisms such as inflammation, sympathetic nervous system activation, and counter-regulatory hormones. Other outcomes will provide hypothesis-generating data to support and direct exploration of these other mechanisms of IR in T1D.

Other potential limitations of this study are:

- (1) Small size: it is possible that a smaller effect will occur in T1D than in other populations and this may therefore be missed in this small sample size.
- (2) The optimal length of time for this intervention is open to debate. Glycemic control changes in type 2 diabetes with metformin occur fairly rapidly (within a few weeks) suggesting that metformin effects on insulin action and glucose metabolism at least, are quite rapid. Most metformin studies in the literature use 3 months of treatment. To minimize subject risk and burden, as well as study costs, I plan to use a 6-week intervention. Evidence certainly supports the expectation that many changes induced by metformin do occur within this time span.
- (3) Limited tracer use: due to cost considerations, only glucose tracer will be used. Ideally glycerol and palmitate tracers would also be used to fully characterize insulin sensitivity of metabolic shifts. Again, these will be considered if a larger study is justified by the preliminary data obtained here.
- (4) Surrogate measures: Outcomes are surrogates that are believed to correlate with vascular disease outcomes. However, a larger and longer study will be required if this study is promising to demonstrate that changes observed with metformin do translate to improved clinical outcomes.
- (5) Changes in glycemic control may occur with metformin despite efforts to avoid this confounder. Separation of effects of insulin sensitization from those of altered glycemic control may be difficult. The study design attempts to minimize this effect by using a relatively low carbohydrate diet, minimizing prandial insulin dosing and thus overall insulin dosing. Subjects will be advised that they may need to decrease insulin dosing on metformin and CGM will be used to monitor glycemic control. This will allow for insulin dose adjustments to maintain prior glycemic control and to avoid hypoglycemia, and for statistical adjustment for any changes in glycemic control that do occur. If improvements in outcomes occur, this will support further exploration of metformin use in T1D regardless of the mechanism.
- (6) Multiple confounders of an analysis of effect on IR also exist, and every effort will be made to minimize the effect of these confounders including emphasis on a stable activity level throughout the intervention periods and exclusion of highly active subjects. Physical stress will be avoided by rescheduling study days as needed for any illness. Efforts to avoid hypoglycemia will include CGM available to the patient and the PI with insulin dose adjustments as needed. In addition, careful statistical analysis of CGM data will be performed to look for and adjust for any effect of hypoglycemia. If present, this underscores the importance of identifying non-glycemic mechanisms involved in IR as complete normalization of glycemia without

hypoglycemia is unrealistic in T1D, especially in an outpatient, lifelong diabetes regimen. Sex hormones also affect insulin sensitivity in women. The age range of particular clinical interest for this study is primarily middle age, including perimenopausal years in women. I have chosen to include perimenopausal women, but not post-menopausal women in this study. One of my future interests is in the disproportionate increase in CVD risk on premenopausal women with T1D. I have powered the current studies adequately to compare responses to the interventions between genders. I am therefore concentrating on women in which I expect to see sex-based differences, that is those in the pre/perimenopausal stages. Hormonal variation will be dealt with in the usual fashion of scheduling visits during the early follicular phase. Estradiol and FSH levels will be checked with baseline labs on all clamp study days to confirm similar hormone levels at all visits. Other confounders such as emotional stress will be difficult to avoid and are present in any study of this type.

F. Data Analysis Plan:

Data collected from each subject will be verified and entered into a computer database. Confirmation of data quality will be performed using computer programs designed to detect errors using accepted ranges, logic checks, and missing values. Outliers will be checked against the original record, and correct values entered into the final data. Data will be transferred into the SAS System Version 8.0 (SAS Institute, NC) for analysis. We plan to use Redcap for data management and SAS for all statistical analysis. Descriptive statistics of all variables at all time points will be derived and reported.

Statistical Analysis Plan: In order to test the effects of metformin on insulin sensitivity, vascular function and compliance (FMD, PWV, AI, and post-occlusion blood flow) in T1D, we will measure insulin sensitivity and vascular parameters in 30 T1D (50% men) after six weeks of metformin and six weeks of placebo in a fixed-order, single-blind cross-over design study. The effect of metformin treatment on insulin sensitivity and vascular function will be assessed by comparing fasting measures at post each period of treatment within study participants using paired t-tests.

CGM data for the final week of the intervention will be analyzed for mean glucose, %>180, %<60, and SD (measure of glycemic variability). Initial analysis will be by paired t-test to assess for differences between the two intervention periods. The impact on insulin sensitivity of CGM parameters that differ between intervention periods will be investigated using a repeated measures mixed effects model with CGM parameters included as time-varying covariates.

Secondary measures (inflammatory, thrombotic, oxidative stress, and endothelial markers, metabolic parameters, autonomic function, and biopsy assays) will be similarly compared. Further, the association of secondary outcomes with vascular function will be analyzed using Pearson correlation coefficients and multivariate linear regression. I plan to use all of the variables that appear to correlate individually in the multiple regression analysis as an exploratory exercise. I recognize that an n of 30 is inadequate to power this model, but will perform this analysis as an exploratory, hypothesis generating exercise. As a further exploratory approach, I plan to use "best 3" and "best 4" best subset regression analyses to identify the variables that are most strongly associated with insulin sensitivity and endothelial function. Subgroup analyses will also be conducted to examine whether metformin affects vascular function in men and women to the same degree.

Power and Sample Size: Power analysis and sample size are based on expected changes from the literature for the primary outcomes FMD and insulin sensitivity.

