COMIRB Protocol

(Use Protocol Manager on the COMIRB Website)

COLORADO MULTIPLE INSTITUTIONAL REVIEW BOARD
[name] [contact] [contact]

Project Title: Effect of Metformin on Vascular and Mitochondrial Function in Type 1 Diabetes

Version date: 6/10/2015

Principal Investigator: [name], PhD

I. Hypotheses and Specific Aims:

Underlying Hypotheses: (1) IR is an important, clinically unaddressed contributor to increased CVD risk in T1D. (2) Treatment of insulin resistance with metformin will improve insulin action, endothelial function, arterial compliance, and mitochondrial function in T1D.

The proposed pilot study is a mechanistic study addressing the hypothesis that the clinically available agent, metformin, widely used as first line therapy in type 2 diabetes, will improve insulin action and vascular function and have the previously unstudied benefit of reducing mitochondrial oxidant generation in T1D. Targeting IR is a novel approach to T1D treatment that may significantly improve current management of T1D and of CVD risk in this high risk population.

Specific Aims:

SA#1: Determine the effect of metformin on insulin sensitivity in T1D.

Hypothesis 1: Metformin will improve insulin sensitivity and insulin signaling in T1D subjects similarly to type 2 diabetic subjects. Approach: T1D subjects (n=30) will have placebo then metformin added to their usual insulin regimen for six weeks in a single-blinded, cross-over design study. Continuous glucose monitoring (CGM) will be performed throughout to allow statistical adjustment for changes in glycemic control and to facilitate insulin dose adjustment to avoid hypoglycemia. Insulin sensitivity will be measured by two-stage (8, 40 mU/m²/min) hyperinsulinemic euglycemic clamp with glucose tracer and insulin signaling will be measured in muscle biopsy samples.

SA#2: Determine the effect of metformin on vascular and mitochondrial sequelae of insulin resistance

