 - arterial stiffness (PWV and AI),
 - CGM measures of hyperglycemia, hypoglycemia, and glycemic variability for one week prior to each clamp,
 - Metabolic (NEFA, lipids, insulin, glucose), inflammatory (IL-6, TNF- α , hsCRP, adiponectin), thrombotic (PAI-1), oxidative stress (urinary isoprostanate, TBARs), and endothelial (ICAM, endothelin-1) markers at baseline each study day,
 - Counter-regulatory hormones (cortisol, growth hormone, glucagon, and catecholamines prior to each clamp,
 - Respiratory quotient at baseline and after low dose insulin infusion,
 - Heart rate variability,
 - Mitochondrial content (DNA and electron transport chain complexes),
 - Mitochondrial function (carbohydrate and lipid oxidation, max state 3 O₂ consumption, uncoupled O₂ consumption),
 - Mitochondrial state 3 O₂ consumption,
 - Mitochondrial oxidant generation (H₂O₂ production, glutathione redox state), and
 - Mitochondrial ATP production/ADP depletion by 31P-MRS.

[figure not shown]
B. Description of Population to be Enrolled: Study Design and Research Methods

Hypotheses: Metformin will improve (1) insulin action, (2) vascular function and compliance, and (3) mitochondrial function and oxidant generation in T1D subjects supporting a therapeutic role for metformin in T1D management, including CVD risk management.

Specific Aims: **Specific Aim 1:** Determine the effect of metformin on IR in T1D. **Specific Aim 2:** Determine the effect of metformin on vascular correlates of IR. **Specific Aim 3:** Determine the effect of metformin on mitochondrial function and oxidant generation.

Overall research plan: I propose to address these hypotheses and aims with a single-blinded, fixed-order, placebo-controlled cross-over design study in T1D subjects. The intervention will consist of 6 weeks of treatment with metformin, separated from the placebo period by a \geq 2 weeks washout period. The fixed order is needed because we and others have found persistent residual effects from metformin treatment, and the necessary washout period is not known. Metformin has been studied to a limited degree in T1D, primarily in terms of glycemic control. It has been found to be safe and well-tolerated in these studies (Vella) and the proposed dose and duration have precedent in the literature. [name] at this institution has performed a study using metformin in T1D youth. From his contact with the FDA, an IND is not required for this study.

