active members) by mass mailing to the full cohort of an IRB-approved letter describing the study, followed by phone calls to invite questions. Although this cohort is an epidemiological outcome cohort, and the initial opinion was that this duration of intervention was inappropriate for such a study, funding pressures have influenced the CACTI PI to consider mechanistic studies and to agree that a short term metformin intervention is acceptable. In fact, a large grant to expand upon this pilot study is currently pending with the NIH. A strength of this study is thus access to the existing NIH-CACTI cohort that has been prospectively studied for ≥ 6 years. This is an active cohort with a great interest in diabetes and its management, and recruitment of 90 subjects for our recent clamp sub-study was easily accomplished.

Study population: The goal is to complete 30 T1D subjects (50% male in each group) for the pilot study. We expect to screen up to 100 subjects to enroll 40 and complete 30. Inclusion criteria:(1)age 20-59 years of age, (2) type 1 diabetes based on antibody-positivity, rapid persistent conversion to insulin requirement after diagnosis, absent C-peptide, or DKA at diagnosis, or a clinical course consistent with T1D, (3) HbA1c 6.0-9.5 (4) willing/able to commit to two 6 week-long study phases, each consisting of blinded medication with blinded CGM, frequent phone follow-up, and 3 days of prescribed diet followed by hyperinsulinemic euglycemic clamp, vascular testing, and 2 muscle biopsies. Exclusion criteria include:

[figure not shown]
- Any comorbid condition associated with inflammation, IR, or dyslipidemia
- Tobacco use
- Pregnancy
- Steroid use
- Scheduled vigorous physical activity >3 days a week
- Angina, known CAD, or any other cardiovascular or pulmonary disease
- A history of COPD or asthma
- Presence of systolic blood pressure >190 at rest or >250 with exercise or diastolic pressure >95 at rest or >105 with exercise
- Untreated thyroid disease
- Proteinuria (urine protein >200 mg/dl) or a creatinine ≥ 1.5 mg/dl(males) or 1.4 mg/dL (females), suggestive of severe renal disease
- Proliferative retinopathy.
- Niacin treatment
- Administration of experimental agent for T1D within 30 days prior to screening
- Recent (prior 6 months) or current metformin or thiazolidinedione use
- Hypoglycemia unawareness or recurrent severe hypoglycemia (no symptoms of hypoglycemia with FSBS<40 and episodes of this severity >1 per week)

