- Weight instability (weight change >5% in last 6 months)
- History of any organ transplant, including islet cell transplant
- Current or prior infection with HIV, hepatitis B or hepatitis C, or transaminases >2x ULN
- Any condition, medical or otherwise that would, in the opinion of the investigator, prevent complete participation in the study, or that would pose a significant hazard to the subject
- History of substance abuse within the 12 months prior to screening

Screening: A phone screen will be followed by provision of the consent form and a screening/enrollment visit at the outpatient CTRC. This visit will include the consent process, history, physical exam, non-fasting screening labs [β -HCG, HbA1c, metabolic panel, TSH, urine microalbumin, and CBC], detailed menstrual history for women, and a DEXA scan for body composition and estimation of caloric needs.

Study design:

T1D subjects (n=30) will have a fixed order of treatment (placebo-metformin) and will be given their first medication after screening is complete and eligibility confirmed. Medications (metformin 500, 1000mg and identical placebo) will be dispensed by the pharmacy and the subject will be blinded to the fixed order of the medications to avoid biased treatment effects throughout the intervention period. As in previous Barbara Davis Center (BDC) metformin studies, this study will use the CTRC pharmacy to dispense the active drug and placebo. Both are provided by Caraco manufacturer. My colleagues at the BDC already purchased tooling for the Caraco brand placebo tablets and the company has agreed to make more placebo tablets for this study as necessary to cut out the upfront cost of tooling.

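### The plan reads a null on both GIR and vascular measures as a sign that T1D differs mechanistically from other populations, which a single-group paired comparison cannot support

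*Combined protocol and SAP*

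**What the plan says.** Section I states the first aim within one population: "Determine the effect of metformin on insulin sensitivity in T1D". Hypothesis 1 then adds a comparison, expecting improvement "in T1D subjects similarly to type 2 diabetic subjects".

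Section IV.B makes type 1 diabetes a condition of entry, and every subject takes placebo first and metformin second. The reason given is that "The fixed order is needed because we and others have found persistent residual effects from metformin treatment". Section IV.F compares the end of each period "within study participants using paired t-tests". Neither section describes a type 2 or non-diabetic group, an external type 2 value, or a margin that would define similarity.

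Section IV.E sets out how results will be interpreted. Improvement in cardiovascular or mitochondrial measures counts in favour of metformin whether or not insulin resistance changes. If GIR and the vascular measures do not change, "this would suggest that IR and CVD risk in T1D are mechanistically different from other populations", and later work would turn to other mechanisms. Limitation (1), in the same section, says that an effect smaller in T1D than elsewhere is possible and that "this may therefore be missed in this small sample size".

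**The concern.** The planned reading of a null takes two steps that the design does not allow. It treats a non-significant paired test as evidence of no effect. It then turns that into a contrast with populations the trial does not observe.

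The protocol itself supplies other explanations for a null:
- a smaller true effect that 30 subjects cannot detect (limitation 1);
- six weeks of treatment, where limitation (2) notes that most metformin studies use three months, as did both studies behind the sample size;
- a fixed order, so that a period effect could offset a drug effect.

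None of these implies a different mechanism. At stake is a false null on both primary outcomes being reported as a finding about T1D biology and used to redirect later research.

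**Working it through.** **Inputs** (section IV.F, Power and Sample Size)
- M/I: difference 0.5 (2.3 − 1.8), SD of the difference 1, n = 30, stated power 75%.
- M/I, unrounded as printed: 0.48, SD 1.09.
- M/I, ten tabulated differences: −2.5, 0.1, 0.55, 0.7, 0.7, 0.7, 2.5, 0.9, 0.4, 0.25. Their sum is 4.30, so the mean is 0.43; the SD is 1.22. They give t = 0.43/(1.223/√10) = 1.11 and p = 0.295, the p-value the plan quotes.
- FMD: SDs 2.1 and 1.9, stated power 80% for a difference of 1.5 points.
- Assumed, because the power section does not state it: two-sided alpha 0.05.

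**Method.** Power of a paired t-test from the noncentral t distribution, with 29 degrees of freedom and noncentrality (difference/SD) × √30.

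**The plan's own figures**
- M/I: 0.5/1.0 × √30 = 2.74, power 75.4% (stated 75%).
- FMD: SD of the difference = √(2.1² + 1.9²) = 2.83, taking zero within-person correlation; for 1.5 points, power 80.1% (stated 80%).

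Both reproduce.

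**Chance that both primaries are falsely null.** The reading in section IV.E needs both GIR and the vascular measures to be null. Taking FMD to represent the vascular measures, and the two outcomes as independent (as section IV.F asserts), the chance is (1 − power for M/I) × (1 − power for FMD):

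| True effects | Miss M/I | Miss FMD | Both missed |
|---|---|---|---|
| M/I 0.5, SD 1.0; FMD 1.5 | 0.246 | 0.199 | 4.9% |
| M/I 0.48, SD 1.09; FMD 1.5 | 0.355 | 0.199 | 7.1% |
| M/I 0.43, SD 1.22; FMD 1.5 | 0.539 | 0.199 | 10.7% |
| M/I 0.25, SD 1.0; FMD 0.75 | 0.737 | 0.711 | 52% |

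**Sensitivity of the first row.** If the outcomes were positively dependent, the joint chance could rise to at most the smaller single miss rate, 19.9%. If the within-person FMD correlation were 0.5, FMD power would be 97.7% and the joint chance 0.246 × 0.023 = 0.6%.

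**What a null could exclude.** The 95% CI half-width at n = 30 is 2.045 × SD/√30.
- M/I: 0.37 (SD 1.0) to 0.46 (SD 1.22). With SD 1.0, an observed difference between 0.13 (0.50 − 0.37) and 0.37 is non-significant yet does not exclude 0.5.
- FMD: 2.045 × 2.83/√30 = 1.06. An observed difference between 0.44 (1.50 − 1.06) and 1.06 is non-significant yet does not exclude 1.5.

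Some nulls would therefore be informative and others not. The plan's reading does not separate them.

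**The case against.** The strongest case against is that the sentence is cautious and sits among the limitations, not in the analysis plan. It suggests rather than asserts, it speaks of other populations without naming type 2 diabetes, and limitation (1) follows with the rival explanation. No test, sample size or stopping decision depends on it, and the study calls itself a pilot. All of that stands, and it limits the weight of the point. It does not make the inference valid, because the caveat is not carried into the reading of a null.

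A reader might infer something stronger: that a false null on GIR alone would be reported as a mechanistic finding, with a probability of 25% on the planning inputs or 54% on the tabulated differences. The documents do not support that. The preceding sentence in section IV.E counts vascular or mitochondrial improvement in metformin's favour even when insulin resistance does not change, so a GIR-only null does not lead to this reading. The 54% is also fragile: it rests on ten values measured from a graph, and without the subject who went from 4.2 to 1.7 the mean difference is 0.76 and the SD 0.70.

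The joint figures may themselves be too high. Vascular measures include PWV and AI as well as FMD, and all would have to be null. At the published FMD change of 5 points (7.4% to 12.4%) the plan states power above 99%, so the joint chance would be below 0.246 × 0.01, about 0.25%.

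Finally, the phrase in Hypothesis 1 can be read simply as rationale. The aims concern T1D alone, and no planned analysis tests similarity.

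**Conclusion.** The point holds for the planned reading of a null on both GIR and vascular measures. One T1D group, compared with itself in a fixed order and tested against zero, cannot show that T1D differs in mechanism from populations outside the trial.

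The chance that the reading is triggered falsely is modest, about 5% to 11%, if the true effects are near the planning values. It is about 52% if both are half as large, which is the kind of situation limitation (1) raises. These figures assume two-sided 0.05, 30 completers, independent outcomes, zero within-person FMD correlation, FMD standing in for all vascular measures, and M/I standing in for GIR.

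The missing type 2 comparator does not undermine the primary comparison of metformin with placebo. The Hypothesis 1 phrase is untested, but nothing in the analysis rests on it.

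**What to change.** Replace the null interpretation in section IV.E with wording such as:

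> If the upper limit of the 95% CI for the metformin-minus-placebo difference lies below a pre-stated reference effect (for FMD, 1.5 points, the difference detectable with 80% power; for GIR, a value to be stated on the GIR scale), we will conclude that an effect of that size is unlikely under these conditions. Otherwise a non-significant result is inconclusive. A null result will not by itself be taken as evidence that T1D differs mechanistically from other populations.

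The investigator must supply the GIR reference value, because the sizing used M/I and the documents give no planning effect for GIR. The rule uses the upper limit so that an interval lying wholly above the reference is not called unlikely.

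The comparison with type 2 diabetes in Hypothesis 1 can be dropped for consistency. Adding a type 2 group is not proposed. As an illustration, on the M/I scale with the same SD of within-person change (1.0 to 1.22) in both groups, detecting a between-group difference of 0.5 with 80% power would need 2 × (SD × 2.80/0.5)², or about 63 to 94 completers per group.

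The cost is a few sentences, with no change to procedures, sample size or tests. The downside is a more modest conclusion after a null.
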